
#### How will you store participant data With participant's direct identifier(s)

#### List the identifier(s) that will be stored

Audio recordings containing participants' voices, and any other identifying information that remains on the recording after participants have been made aware of/exercised their right to erase the recording, will be stored electronically, labeled with the participant-generated ID number. Regarding participants who agree to be contacted for future studies - we will store this contact information in a separate password protected file, on our secure online password-protected server. We will assign a new ID number to the current participant's study ID number. Participant's contact information will be stored with this new ID. The file that links participants' contact information and new ID will be

stored in a separate password protected file, on the secure online password-protected lab server. The document that links both ID numbers will be password protected and stored in a separate password-protected file on the secure online password-protected lab server. If an individual requests their contact information be removed, we will remove their contact information from our database. Participant contact information will only be accessible to approved personnel.

# Will identifiers be deleted (and data No anonymized) at a later date?

-	Retain data for three years, or longer when		
the research has been completed?	required by the study sponsor, then destroy		
	it.		

Page 34 of 36

2021-0291

**[name]** 

Page 36 of 36

Statistical Analysis Plan

"Empowerment Self-Defense Training for the Prevention of Victimization of Transgender Women" ID: R21MD014807 NCT04934189 1/18/2023

Statistical Design and Power

This R21 will use a non-experimental pilot study of 3 groups of 16 transgender women to assess preliminary feasibility and acceptability. A fully powered randomized controlled trial is neither practical nor advisable in this R21. The decision to use a single group, non-randomized design, rather than a randomized controlled trial (RCT), is best considered in light of critiques regarding the use of pilot RCTs to guide decision-making about whether to pursue larger-scale RCTs.⁷⁴⁻⁷⁶ The central point of these critiques is that because of their small size, pilot RCTs provide imprecise data on effect sizes, which can lead to both Type I and Type II errors. As a result, subsequent RCTs that are based on pilot RCTs may be underpowered (e.g., if pilot RCT suggests an artificially large effect size for the treatment [Type I error]) or not pursued (e.g., if pilot RCT suggests an artificially small effect size [Type II error]) even if the treatment could actually have been effective.⁷⁵ On the other hand, pilot trials do provide valuable information on the feasibility of study procedures, including recruitment, retention, implementation of the intervention, and data management. As the key objectives of this R21 are to develop the ESD self-defense training tailored for TW (Aim 1) and to assess its preliminary feasibility and acceptability (Aim 2), we will maximize the amount of useful information that can be gained about study feasibility and treatment efficacy in order to guide a future RCT of the new tailored violence prevention curriculum.

Data Management. Following the CONSORT statement,⁸² we will track how many participants: (a) are told about the study; (b) are screened for the study; (c) do and do not meet inclusion criteria; (d) are invited to participate; and (e) actually enroll. Pre-inclusion attrition rates may reveal potential enrollment bias. To explore how differential refusal may affect generalizability of findings, we will also record the reasons for exclusion from and refusal to participate in the study. As recommended by the IOM Report,⁸³ we will model the effects of dropout patterns as data not missing at random using Bayesian analysis utilizing a pattern-mixture modeling approach. We will consider scale transformations, such as log, to decrease the effect of outliers.

Feasibility Analyses. The primary target outcomes of Aim 2 will be completion of the pilot study at the target recruitment total (n = 48), with < 25% dropout from assessments (Table 1. Research Plan). Secondary target outcomes related to assessment procedures, acceptability of the intervention, and laboratory and data management are detailed in Table 1 of the Research Plan. Successful completion of the pilot trial, including meeting or exceeding these benchmarks for success, will support the feasibility and acceptability of recruiting participants into a future RCT of the tailored ESD intervention using similar procedures and a similar population.

Power Analyses. Preliminary efficacy of the tailored ESD violence prevention intervention will be evaluated as an exploratory aim via administration of the battery of validated questionnaires assessing 1) behavior change variables (i.e., use of resistance tactics, self-protective behavior, and assertive relational communication); 2) psychological variables hypothesized to mediate the effects of the intervention on behavior (i.e., resistance self-efficacy, attributions of self-blame, rape myth acceptance, gender minority risk and resilience factors); and 3) reductions in rates of exposure to victimization) at baseline, post-intervention, and at the 3- and 6-month follow-up assessments.

Given its modest size and aims, this pilot is not powered to detect reductions in victimization exposure. Nonetheless, we will conduct exploratory analyses to evaluate potential trends that may emerge for the effects of treatment on behavior change, violence risk and resilience variables, and victimization.

A power analysis was performed using the R package WebPower for a representative variable for each these three outcomes categories. Sample size can be derived based on effect size (f) and power (1- β). Here f= σ_m/σ , Cohen (1988, p. 275), σ_m is the standard deviation of population means and σ the standard deviation within the populations. Even though Cohen (1988) provides general magnitudes for small effect size: f = 0.1, medium effect size: f = 0.25, large effect size: f = 0.5, he argues that these guidelines are to be used when there is insufficient prior knowledge and "may not be reasonably descriptive in any specific area." The preliminary efficacy results derived from the proposed pilot trial will further inform our estimate of an effect size

of clinical interest for these outcomes. This information will be used to plan for a sufficiently powered confirmatory trial (e.g., R01).

1. Behavior Change Variable: use of self-protective behavior

Test procedure: paired two-sample t-test, one-sided, $\alpha = 0.05$, $s_d = 8$

Power calculation: GPower

	Power				
Effect Size (ES)	0.8	0.85	0.9	0.95	
1	398	462	550	694	
1.5	178	206	245	310	
2	101	117	139	175	
2.5	65	75	90	113	
3	46	53	63	79	

2. Attitudinal Mediator Variable: self-efficacy

Test procedure: paired two-sample t-test, one-sided, $\alpha = 0.05$, $s_d = 8$

Power calculation: GPower

	Power				
Effect Size (ES)	0.8	0.85	0.9	0.95	
1	398	462	550	694	
1.5	178	206	245	310	
2	101	117	139	175	
2.5	65	75	90	113	
3	46	53	63	79	

3. Reductions in Exposure to Victimization Variable: sexual victimization reduction

Test procedure: chi-square test for independence, two-sided, df = 2, α = 0.05

Power calculation: R package powerAnalysis

	Power				
Effect Size (ES)	0.8	0.85	0.9	0.95	
0.1	964	1093	1266	1545	
0.2	241	274	317	387	
0.3	108	122	141	172	
0.4	61	69	80	97	
0.5	39	44	51	62	

Inferential analyses. We will use repeated measures one-way ANOVA to test if the tailored ESD curriculum has statistically significant effect on measures of behavioral and psychological/attitudinal change. If a significant effect is detected, we will use Tukey's pairwise-comparison procedure to compare all treatment means, with a 95% family confidence coefficient. To assess changes in exposure to victimization, we collapse into three levels: (a) no history of victimization; (b) moderate victimization; (c) severe victimization. For this categorical data, a chi-square test of independence will be performed to compare post-treatment vs. pre-treatment, 3-month FU vs. pre-treatment, and 6-month FU vs. pre-treatment respectively to assess the preliminary efficacy of the program, with a family-wise type I error controlled at 0.05 using Bonferroni procedure.

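### SAP tables 1 and 2 size a one-sided paired t-test, so their n does not give the tabled power for any one specified pair under the planned Tukey comparisons

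*SAP*

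**What the plan says.** The SAP's Power Analyses section takes one representative variable per outcome category. For the behavioral variable (table 1) and the attitudinal mediator (table 2) it names "Test procedure: paired two-sample t-test, one-sided", with alpha 0.05 and s_d = 8. The two tables are identical. For an effect of 3 they give n = 46, 53, 63 and 79 for power of 80, 85, 90 and 95%.

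The SAP's Inferential analyses section, repeated in Protocol section 5, tests these outcomes by repeated-measures one-way ANOVA. If that is significant, it applies Tukey's "pairwise-comparison procedure to compare all treatment means, with a 95% family confidence coefficient". No one-sided t-test appears there, and no power figure is given for the ANOVA or for the Tukey step.

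The text above the tables defines effect size as Cohen's f, with benchmarks up to "large effect size: f = 0.5". The SAP lists four assessments (baseline, post-intervention, 3 and 6 months); Protocol section 6 lists three, without the 3-month one. The pilot's results are to be carried forward: "This information will be used to plan for a sufficiently powered confirmatory trial".

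**The concern.** The tables and the analysis describe different tests. Tukey intervals for all pairs are two-sided by construction and share one 5% error rate among three pairs (three assessments) or six (four). The tabled test is one-sided and spends the whole 5% on a single comparison. A reader who takes 80% from table 1 or 2 as the chance of detecting a given change, for example baseline to post-course, in the planned analysis will be too optimistic. A non-significant pair would then count more heavily against the intervention than it should when the next trial is planned.

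The label invites a second misreading. The effect sizes of 1 to 3 in tables 1 and 2 are not values of f; they reproduce only as raw points on a scale whose change has SD 8.

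**Working it through.** **Inputs.** One-sided alpha 0.05, s_d = 8 and differences d of 1 to 3 (SAP tables 1 and 2); Tukey at 95% family confidence (SAP Inferential analyses); n = 48 and the criterion "with < 25% dropout from assessments" (SAP Feasibility Analyses); k = 3 assessments (Protocol section 6) or k = 4 (SAP). The smallest n that meets the dropout criterion is 37: 11/48 = 22.9% lost, whereas 12/48 is exactly 25%. Assumptions made here: SD 8 for the difference between every pair of assessments (sphericity), and 37 treated as complete cases, although the SAP plans pattern-mixture modelling of dropout.

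**1. The plan's own figures.** Power is the probability that a noncentral t with n − 1 degrees of freedom and noncentrality δ = (d/8)√n exceeds the one-sided 5% critical value. For d = 3 and n = 46, δ = 0.375 × √46 = 2.54, the critical value is 1.68 and power is 80.5%. All 20 cells of table 1, and so of table 2, reproduce exactly. The effects are therefore raw points, from 1/8 = 0.125 to 3/8 = 0.375 SD of change.

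**2. One specified Tukey pair.** With SD 8 for every pair the error variance is 64/2 = 32, and the standard error of a pairwise difference is √(2 × 32/n) = 8/√n, so δ is unchanged. The critical value becomes q(0.95; k, (n − 1)(k − 1))/√2. At n = 46 this is 2.38 for k = 3 and 2.60 for k = 4. A two-sided unadjusted t-test, with critical value 2.01, would give 70.2%.

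Power for a 3-point change:

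| n | δ | One-sided t (as tabled) | Tukey pair, k = 3 | Tukey pair, k = 4 |
|---|---|---|---|---|
| 46 | 2.54 | 80.5% | 56.5% | 47.9% |
| 48 | 2.60 | 82.0% | 58.7% | 50.1% |
| 37 | 2.28 | 72.3% | 46.0% | 37.5% |

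The n for 80% is 74 (k = 3) or 84 (k = 4), not 46. Across the tables, the columns headed 80, 85, 90 and 95% give about 56, 63, 72 and 83% for k = 3, and about 47, 55, 64 and 77% for k = 4.

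**3. Difference detectable at 80% power.** One-sided t-test: 2.91 points at n = 48 and 3.33 at 37. One Tukey pair: 3.73 and 4.27 (k = 3), or 3.98 and 4.55 (k = 4). Divided by 8, the Tukey figures are 0.47 and 0.53, or 0.50 and 0.57, SD of change.

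**4. The ANOVA step.** Requiring a significant omnibus test as well as the specified pair lowers power slightly. By simulation it is 57–58% / 48–50% at n = 48 for k = 3 / k = 4, and 44–46% / 36–37% at 37. Omnibus power itself depends on the mean profile, through noncentrality nΣ(μ − μ̄)²/32. At n = 48, with a largest difference of 3 points:

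- k = 3: from 62% for (0, 3, 1.5), noncentrality 48 × 4.5/32 = 6.75, to 76% for (0, 3, 3), noncentrality 48 × 6/32 = 9.
- k = 4: from 56% for (0, 3, 1.5, 1.5), noncentrality 6.75, to 87% for (0, 0, 3, 3), noncentrality 48 × 9/32 = 13.5.

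**5. If sphericity fails.** Baseline-to-post pair, SD 8, pooled-error Tukey, n = 48, by simulation, k = 3 / k = 4:

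- Other pairs more variable (autoregressive correlation 0.5 to 0.9): 46–52% / 26–37%.
- Other pairs less variable (SD 8 for each contrast with baseline, SD 6 down to 3 between post-course assessments): about 65–72% / 61–73%, to within about one percentage point of simulation error.

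Both patterns are assumptions; the documents support neither over the other. All these figures lie below the t-test's 82%.

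**The case against.** The tables name their test openly and never claim power for Tukey, so they mislead only a reader who transfers the numbers. What goes forward to the next trial is an effect-size estimate, and the Tukey intervals will show the precision of each pair. Efficacy is exploratory, the tables commit to no cell, and neither n = 48 nor the feasibility criterion is derived from them. If the course dates in Protocol section 6 held (last session 12/19/21), 6-month follow-up ended around June 2022, before the SAP date of 1/18/2023, so new tables could not change conduct. All of this stands and limits the severity. It does not remove the mismatch: these are the only power figures offered for the scale outcomes, and they belong to a test that is not planned.

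Three stronger readings are tempting, and the documents do not support them.

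- *The tables are miscalculated.* They are not; every cell reproduces.
- *Every result of the plan has less power than tabled.* With four assessments and means (0, 0, 3, 3), omnibus power at n = 48 is 87%, above the t-test's 82%. The shortfall shown here is for specified pairs.
- *The protocol is wrong to say that efficacy is powered for large effects.* For the scale outcomes, at the SAP's own large f of 0.5, omnibus power is at least 99.8% even at n = 37 with no correlation between assessments.

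**Conclusion.** The point holds as a minor inconsistency. For one specified pair and a 3-point change, the planned analysis has roughly 24 (k = 3) to 33 (k = 4) percentage points less power than tabled at n = 46 (80.5 − 56.5 = 24.0; 80.5 − 47.9 = 32.6). The size of the gap rests on SD 8 for every pairwise difference and moves in both directions if that fails; the direction held in every case examined. The n = 37 figures also rest on complete cases. It would go too far to infer that the pilot is too small or should change: its primary outcomes are recruitment and retention. What is affected is how much weight a non-significant pair should carry in planning the confirmatory trial.

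**What to change.** Keep n = 48 and the planned ANOVA and Tukey analysis.

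1. Replace tables 1 and 2 with the difference detectable at 80% power for one specified Tukey pair, or relabel them as one-sided, unadjusted t-test figures and add these differences beside them. State that they are conditional on s_d = 8 for all pairs and on the analysed n: about 3.7 points (0.47 SD of change) at 48 and 4.3 (0.53) at 37 with three assessments, or 4.0 (0.50) and 4.5 (0.57) with four.
2. Reconcile the assessment count (protocol three, SAP four) and use the set that then applies.
3. Label the effect sizes in tables 1 and 2 as raw points, distinct from f. Keep the f benchmarks, because they are the only anchor for the protocol's reference to large effects.
4. If a sphericity sensitivity is shown, give both directions. Do not substitute Bonferroni-adjusted t-tests, which are not planned for these outcomes either.

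Optional editing: the text says "A power analysis was performed using the R package WebPower", while tables 1 and 2 name GPower and table 3 names powerAnalysis. Table 3 uses alpha 0.05, although the victimization contrasts are to be run "with a family-wise type I error controlled at 0.05 using Bonferroni procedure"; a footnote would do, since the SAP already disclaims power for victimization.

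The cost is a revised table and some wording in the SAP's power section. Enrolment, analysis and the feasibility criterion do not change. The stated figures become less favorable.

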**Initial Application** 

**[name]** 

## 5. Research Design - Overview

## **Research Purpose and Hypothesis**

This study leverages the strong evidence-base for Empowerment Self-Defense (ESD) violence prevention to address disparities in violence exposure among TW. The overarching goal of this R21 is to develop and refine a tailored ESD violence prevention training for diverse TW through a series of sequential Aims: a) develop an initial draft of an ESD violence prevention curriculum tailored to TW (Aim 1) (See protocol number 2020-0017); b) evaluate the feasibility and acceptability of recruitment, assessment procedures, retention and follow-up procedures, and implementation of the new intervention (Aim 2); and c) assess the preliminary efficacy of the tailored intervention program to increase use of self-protective resistance strategies, mitigate minority stressors and attitudinal barriers to self-defense, and reduce rates of exposure to violence (Exploratory Aim). Together, the proposed research will lay the foundation for a large-scale randomized controlled trial (RCT) of the tailored ESD violence prevention curriculum. We will accomplish these aims using a two-phase research design that begins with formative qualitative work engaging research partners on a community board and a small sample of research participants (See protocol number 2020-0017). This data will be used to inform the development and refinement of the ESD violence prevention curriculum for TW. Further refinement and assessment of the feasibility and acceptability of the curriculum will occur in Phase 2 through the delivery of the tailored ESD curriculum to 3 groups of 16 TW. To assess the preliminary efficacy of the tailored intervention, program participants will complete a brief survey assessing the program directly after completion, as well as a battery of validated questionnaires assessing use of resistance strategies, gender-minority and general psychological factors hypothesized to mediate the behavioral effects of the intervention, and exposure to victimization experiences prior to, immediately following, and 6 months post-completion of the training.

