
Scale- Conflict Tactics Scale - Gender Minority Stress Risk and Resilience Scale - Post Traumatic Stress Disorder Symptom Checklist for DSM-5 (PCL-5)- Sexual Assertiveness Questionnaire- Resistance Tactics Survey- Dating Self-Protection - Illinois Rape Myth Acceptance - Resistance Self-Efficacy - Personal Progress- Transgender Congruence Scale - Depression Anxiety and Stress Scale - Quick Drinking Screen - DAST-10Brief acceptability checklists will be administered after each course session, which will contain a brief list of topics covered during that training session and participants will indicate which of the topics they felt were adequately covered (See page 38 of Assessment Packet, "Satisfaction and Fidelity Forms" for example items and formatting of this checklist). Lastly, an exit interview will be scheduled on the final day of the course, and will take place over the weeks immediately following the completion of the course. Interviews will be video recorded using the Zoom videoconferencing platform. The video-recorded qualitative interviews will be recorded and transcribed verbatim using the Zoom transcription function (omitting identifying information) and verified for accuracy. We will use three strategies to improve retention, based on an intensive evidence-based follow-up protocol with which the PI has considerable experience. First, participants will be compensated for completion of the assessment appointments at increasing increments over time (i.e., \$40 for baseline, \$30 for follow-up immediately after the course and \$30 for the exit interview after the course, \$80 for 6-month follow-up). Second, at baseline, participants will be asked to provide extensive locating information and to provide names of two local persons to be contacted in the event that the participant cannot be reached. This information will be updated at the time of follow-up survey administration. Third, participants will receive \$10 cash for each of the five session acceptability checklists they complete (one per session attended- up to \$50 total) which will be distributed at session 3/5 (up to \$30) and 5/5 (up to \$20). Analyses will be of two primary types: (a) examinations of whether feasibility targets were met across a variety of measures; and (b) examinations of the efficacy of the tailored ESD violence prevention intervention. We will use repeated measures one-way ANOVA to test if the tailored ESD curriculum has statistically significant effect on measures of behavioral and psychological/attitudinal change. If a significant effect is detected, we will use Tukey's pairwise-comparison procedure to compare all treatment means, with a 95% family confidence coefficient. To assess changes in exposure to victimization, we will collapse into three levels: (a) no history of victimization; (b) moderate victimization; (c) severe victimization. For this categorical data, a chi-square test of independence will be performed to compare posttreatment vs. pre-treatment, and 6-month FU vs. pre-treatment respectively to assess the preliminary efficacy of the program, with a family-wise type I error controlled at 0.05 using Bonferroni procedure. Our efficacy outcomes are exploratory and powered to detect large effect sizes. In the largest scale RCT of an ESD violence prevention program to date, rates of completed assault among women receiving resistance training were reduced by half at 1-year follow-up. However, as there are no existing studies that report on ESD efficacy among TW, we will use results of our exploratory efficacy analysis to shape power analyses for a subsequent, fully powered, RCT

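### The only planned victimization test ignores the order of the three levels and gives no signed effect estimate, although the aim is a reduction in exposure

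*SAP*

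**What the plan says.** The Protocol (Research Purpose and Hypothesis) gives, as an exploratory aim, lowering rates of exposure to violence. The SAP (Power Analyses) lists the outcome as "reductions in rates of exposure to victimization".

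The SAP (Inferential analyses) then states that "we collapse into three levels: (a) no history of victimization; (b) moderate victimization; (c) severe victimization". It applies a chi-square test of independence to "post-treatment vs. pre-treatment, 3-month FU vs. pre-treatment, and 6-month FU vs. pre-treatment respectively", with Bonferroni control at 0.05. The Protocol (Research Design and Methodology) has the same three levels and the same test but only two comparisons: "compare posttreatment vs. pre-treatment, and 6-month FU vs. pre-treatment". The SAP sizes the outcome in its third power table as "chi-square test for independence, two-sided, df = 2, α = 0.05".

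Neither document gives cut-points for moderate and severe, a look-back period, an ordinal or paired test, a count or rate model, a signed effect estimate, or a rule on direction. The SAP says that the pilot is not powered for victimization, that it will look for trends, and that its efficacy results will inform the effect size for a confirmatory trial.

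**The concern.** The aim has a direction and the test has none. A chi-square on 2 degrees of freedom asks only whether two distributions over three labels differ. It gives the same answer however the labels are ordered, and a significant result can arise with no net shift in severity.

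The coding also discards frequency. If a woman's level is set by her worst reported act (an assumption, since cut-points are not given), falling from six severe incidents to one leaves her in the same level.

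At stake is what this pilot passes on. A chi-square statistic supplies neither a trend nor a rate ratio from which to plan the later trial.

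**Working it through.** **1. The plan's own table.** For a chi-square test, N = λ/w², where λ is the noncentrality for 2 df. At α = 0.05 and 80% power, this gives 963.5, 240.9, 107.1, 60.2 and 38.5 for w = 0.1 to 0.5. The SAP prints 964, 241, 108, 61 and 39. All 20 cells reproduce, so the sizing arithmetic is sound for the test chosen.

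**2. Direction.** With equal row totals, the expected count in each column is the mean of its two cells, and on 2 df p = exp(−χ²/2).
- 9/19/9 to 16/5/16 (n = 37): expected 12.5, 12, 12.5. χ² = 2(3.5²/12.5) + 2(7²/12) + 2(3.5²/12.5) = 1.96 + 8.17 + 1.96 = 12.09, p = 0.002. Scoring the levels 0, 1, 2, mean severity is (19 + 18)/37 = 1 before and (5 + 32)/37 = 1 after.
- 10/18/20 to 22/18/8 (n = 48): expected 16, 18, 14. χ² = 2(6²/16) + 0 + 2(6²/14) = 4.50 + 5.14 = 9.64, p = 0.008. The reverse shift, a worsening, gives the same χ² and the same p.

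**3. Lost frequency.** If every woman fell from 6 to 3 moderate incidents, no level would change and χ² would be 0.

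**4. Power when incidents halve.** From the documents: 48 women, about 36 at the 25% dropout limit (48 × 0.75), and per-test α of 0.05/3 = 0.0167 (SAP) or 0.05/2 = 0.025 (Protocol). The benchmark is the Protocol's statement that "rates of completed assault among women receiving resistance training were reduced by half at 1-year follow-up".

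Assumed, because the documents give none of it: incident means, between-woman spread (Poisson counts with a gamma frailty), share of incidents that are severe, equal look-back windows, and level set by the worst act.

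| Setting | Planned χ² | Paired signed-rank, ordered levels | Paired signed-rank, counts |
|---|---|---|---|
| n = 36–48, mean 1–6, 40% severe, α 0.0167 | 6–14% | 13–43% | 24–100% |
| n = 48, mean 2, 20% severe, α 0.0167 | 13.5% | 41% | 87% |
| n = 37, mean 2–6, 40% severe, extra variation between periods, α 0.025 | 10–12% | 24–26% | 48–66% |
| n = 37, mean 1, otherwise as above | 11% | 19% | 30% |
| n = 48, mean 1–8, 20% severe, wider range of variation between periods, α 0.0167 | 6–12% | 10–31% | 15–80% |
| n = 48, mean 0.25, 20% severe, α 0.0167 | 5% | 9% | 12% |

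The first two tests use the same three levels, so the step between them reflects pairing and order together. The step from the second to the third is the cost of collapsing. With no true change, none of the three tests materially exceeded its nominal level.

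The low power of the planned test follows from the small shift. In the second row the levels move from 33/38/29% to 50/33/17%, w = 0.18. Even counting 48 women as 96 independent observations, 80% power needs w = √(λ/96) = 0.32 at α = 0.05, or 0.36 at α = 0.0167.

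**5. Power when the share of women exposed halves.** Moderate and severe are assumed equally common, with 96 independent observations and α = 0.0167. For baseline prevalence 20%, 40%, 60% and 80%, w is 0.14, 0.22, 0.30 and 0.41, and planned power is 11%, 30%, 61% and 90%. With 72 observations (36 women) at 60% and 80% prevalence it is about 45% and 78%.

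**The case against.** A reader might infer that a real halving of violence would mostly be missed. The documents do not support that as a general statement. They never say whether the rate means incidents per woman or the share of women exposed. On the second reading, with high baseline prevalence, step 5 shows that the planned test is not weak. The gain from counts also rests on assumed incident means and spread, and it nearly disappears when incidents are rare. Part of the contrast between the planned test and a count analysis is loss from ignoring pairing, not from collapsing.

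A reader might also infer that the plan would credit a worsening as efficacy. Any two-sided test can be significant for a worsening, the SAP labels this one two-sided, and the direction is visible in the table. What stands is narrower: the plan names no signed estimate and no rule for reporting direction, and an unordered test can be significant with no net shift.

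A total count has its own blind spot. If resistance turns a severe incident into a moderate one, the level may change while the count does not.

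Finally, the SAP openly disclaims power for victimization, and the feasibility benchmarks are recruitment and retention. That limits the consequence, but it does not explain using an analysis that returns neither a trend nor an effect size, when the SAP wants both.

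**Conclusion.** The point holds in a limited form. The planned analysis ignores level order, gives no signed effect, and cannot see change within a level, so a significant result need not mean a reduction. This follows from the text and from the exact tables in step 2.

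The size of the power loss is conditional. If incidents halve at a mean of 1–6 per window with 40% severe, power at α = 0.0167 is about 6–14% as planned, 13–43% with ordered and paired levels, and 24–100% with counts. At a mean of 0.25 (20% severe, n = 48) none of the three exceeds about 12%. If the share of women exposed halves from 60–80%, planned power at n = 48 is 61–90%. The outcome is exploratory, so the main loss is information for planning the later trial.

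**What to change.** In the SAP (Inferential analyses) and the Protocol (Research Design and Methodology):

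- Treat the three levels as ordered and paired within woman, for example by a signed-rank test, and report the direction and size of change with a 95% confidence interval.
- Define the cut-points and use equal look-back windows.
- State whether the rate means incidents per woman or the share of women exposed.
- If the instruments record frequency, add a paired analysis of incident frequency with a rate ratio and confidence interval. If they record only separate items, use the number of incident types endorsed; the power figures for counts do not carry over to that measure. Report either alongside severity, not in place of it.
- Reconcile the number of follow-up comparisons, since it sets the Bonferroni divisor.

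The cost is SAP and Protocol wording and slightly more analysis work. The ordered, paired analysis needs no new data items. Whether frequencies exist must be checked against the assessment packet, and skewed counts need a rank or count model.
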